# 2. OBJECTIVES

Primary Objective:

 To assess the antibody based immune response after vaccination against COVID-19 in patients with cancer treated with immunotherapy and/or chemotherapy as compared to controls

Secondary Objectives:

- To assess adverse events (AEs) after vaccination against COVID-19 in patients with cancer treated with immunotherapy and/or chemotherapy
- To assess durability of the antibody response in patients with cancer treated with immunotherapy and/or chemotherapy
- To analyze the SARS-CoV-2 specific T cell response after vaccination in patients with cancer treated with immunotherapy and/or chemotherapy

Exploratory Objectives:

- To perform in-depth analysis of cellular immune responses in patients with cancer treated with immunotherapy and/or chemotherapy
- To identify baseline (immune) parameters associated with vaccination response in patients with cancer treated with immunotherapy and/or chemotherapy
- To assess the neutralizing capacity of antibodies against SARS-CoV-2 after vaccination in patients with cancer treated with immunotherapy and/or chemotherapy
- To analyze induction of mucosal antibodies against SARS-CoV-2 in mucosal lining fluid samples. To describe the incidence of SARS-CoV-2 infection, outcome of COVID-19 during 12 months after vaccination in patients with cancer treated with immunotherapy and/or chemotherapy
- To analyze SARS-CoV-2-binding antibody concentration after a third vaccination in participants without an adequate antibody response after two vaccinations
- To analyze safety of a third vaccination

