To evaluate vaccination related AEs, patients will be asked to collect solicited local and systemic AEs for 7 days after each vaccination using a questionnaire. Similarly serious AEs (SAEs) will be collected for 7 days after each vaccination. Most patients who receive systemic cancer treatment experience multiple AEs that are cancer treatment related, or disease related. As vaccination related AEs are mainly expected within the first week after vaccination, it is not useful to collect all AEs for a prolonged period. Instead, all newly occurring immune related AEs (irAEs) are collected for the immunotherapy and chemo-immunotherapy cohorts (B and D) up to 28 days after the second and if applicable the third vaccination. irAEs are toxicities from immune checkpoint inhibitors and do not include infusion reactions [38]. Furthermore, adverse events of special interest (AESIs) will be collected for the duration of the study in the patient cohorts.

Information on incidence of SARS-CoV-2 infection, outcome of COVID-19 during 18 months after the second vaccination will be collected using questionnaires. For the study participants who give separate consent, information on positive corona tests during the study will also be collected from the RIVM.

Although this study is not powered to detect differences in protection against COVID-19 between patients and controls, information on incidence of SARS-CoV-2 infection, outcome of COVID-19 will be collected up to 18 months after the second vaccination for descriptive purposes.

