## Correction for drop-out

We expect that a proportion of the participants will already have SARS-CoV-2 antibodies at baseline and will not be evaluable for the primary endpoint. In addition, we anticipate that there will be a drop-out of participants at later time points. Reasons for drop-out may include death or poor performance status as a result of progressive malignancy and/or cancer treatment related AEs. Therefore, we will correct for non-evaluable patients by increasing each cohort with 20%. This means that 246 participants will be recruited in cohorts A, C and D, and 135 participants will be enrolled in cohort B. In total, 873 participants (627 patients and 246 individuals without cancer) will be included.

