# 8.1.3 Exploratory study parameters

- In-depth flow-cytometric analyses for functional and phenotypical characterization of SARS-CoV-2 specific cellular immune responses will be performed followed by assessment of proliferative capacity, cytokine production and phenotypical markers in a subset of patients
- To determine baseline (immune) parameters associated with immune response to COVID-19 vaccination
- To assess the induction of SARS-CoV-2-specific antibodies in mucosal lining fluid
- Neutralizing capacity of antibodies to test functionality.
- Information on incidence of SARS-CoV-2 infection, outcome of COVID-19 will be collected and reported during 18 months after the second vaccination. To this end, questionnaires will be used. Information on positive corona tests during the study will also be collected from the RIVM.
- To analyze SARS-CoV-2-binding antibody concentration after a third vaccination in participants without an adequate antibody response after two vaccinations on day 28 after the third vaccination.
- To analyze safety of a third vaccination as indicated under 8.1.2
- To assess SARS-CoV2 specific T cell response at 28 days after the third vaccination

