#### 10.3 Other study parameters

- Dynamics of SARS-CoV-2 specific antibody concentrations will be analyzed, e.g. by calculating geometric mean fold-rise between baseline and post-baseline time points and antibody decay after day 28.
- In-depth flow-cytometric analyses for functional and phenotypical characterization of SARS-CoV-2 specific cellular responses will be performed by assigning proliferative capacity, cytokine production and phenotypical markers (>25 markers in parallel) in a subset of patients. These descriptive study parameters will not be statistically compared between cohorts.
- Baseline (immune) parameters will be related to vaccination response using univariate analysis.
- As a functional readout, the neutralizing capacity SARS-CoV-2 antibodies will be measured at baseline, 28 days and 6, 11 and 18 months after the second vaccination. Titers will be expressed as GMCs with 95% CIs for each cohort, for each time point.
- To assess induction of a mucosal antibody response, mucosal lining fluid samples will be collected for measurement of SARS-CoV-2-specific antibody concentrations with multiplex immunoassay at baseline and at 28 days after the second vaccination. Additional analyses e.g. neutralizing capacity of mucosal antibodies can be performed.
- Mucosal SARS-CoV-2-specific antibody response will be correlated with serum SARS-CoV-2-specific antibody response.

- Information on incidence of SARS-CoV-2 infection, outcome of COVID-19 during 18 months after the second vaccination will be collected. The number of participants tested, the number of SARS-CoV-2 tests and test results will be reported. For participants with a positive test, information about severity will be presented including hospital admissions, use of oxygen, intensive care admission and mechanical ventilation.
- Levels of SARS-CoV-2 S-specific IgG antibodies before the third vaccination, and at day 28 after the third vaccination will be measured to assess antibody response in participants with an inadequate response to two mRNA-1273 vaccinations.
- Safety of a third mRNA-1273 vaccination in participants with an inadequate response to two mRNA-1273 vaccinations as mentioned under 10.2.

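### Section 10.3 plans counts of SARS-CoV-2 tests and results without follow-up time, although the objective is incidence; if patients are followed for less time than controls, the counts can understate their infections relative to cohort A

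*Combined protocol and SAP*

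**What the plan says.** Among the exploratory objectives, section 2 lists: "To describe the incidence of SARS-CoV-2 infection, outcome of COVID-19 during 12 months after vaccination in patients with cancer". Section 1.5 also names the infection rate as something the trial will assess. Section 10.3 sets the window: "Information on incidence of SARS-CoV-2 infection, outcome of COVID-19 during 18 months after the second vaccination will be collected". It then states what will be shown: "The number of participants tested, the number of SARS-CoV-2 tests and test results will be reported". For participants with a positive test it adds severity (admission, oxygen, intensive care, ventilation). Unlike several items in section 10.2, this one does not say that results will be given per cohort.

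Infections are found in two ways. All participants complete questionnaires, and section 3 adds a registry source for some of them: "For the study participants who give separate consent, information on positive corona tests during the study will also be collected from the RIVM".

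On follow-up, the drop-out paragraph of section 4.4 says: "Reasons for drop-out may include death or poor performance status as a result of progressive malignancy". Section 4.2 requires a life expectancy of more than 12 months. On status, section 3 says: "Although this study is not powered to detect differences in protection against COVID-19 between patients and controls", and calls the data descriptive.

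**The concern.** Incidence needs a population at risk and a time over which it was observed. Section 10.3 supplies neither. The only group it names is participants tested, and positives divided by participants tested is test positivity, not incidence. The cohorts also differ in size (240, 131, 229 and 143 evaluable in A to D, section 1.6), so bare counts cannot be read side by side.

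If patients die or leave earlier than the partners in cohort A, even a proportion of those enrolled gives patients fewer months in which an infection could be recorded. At the same underlying risk they would then show fewer infections, which could be read as equal or better protection. These are the only planned data on clinical protection against COVID-19. Cohort A was included for comparison, so readers are likely to compare cohorts even though no test is planned.

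**Working it through.** The plan gives no incidence, person-time or loss by cohort, so there is no figure of its own to reproduce. Its 20% allowance (112 × 1.2 = 134.4, rounded up to 135; 205 × 1.2 = 246) is the same for every cohort and also covers baseline seropositivity. It says nothing about 18-month loss by cohort.

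**Inputs**
- From the plan: horizon 18 months (section 10.3); 246 planned in cohort A and in cohort C.
- Assumed: loss by 18 months of 5% in controls and 30% (range 20% to 40%) in patients; equal true risk and equal detection; loss unrelated to infection.

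**Constant risk, simple form.** With even loss, the share of the full observation time retained is 1 − loss/2. The crude patient/control ratio as a multiple of the true ratio is:
- 20% loss: 0.90 / 0.975 = 0.92
- 30% loss: 0.85 / 0.975 = 0.87
- 40% loss: 0.80 / 0.975 = 0.82

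**Constant risk, hazard form.** Let l be the monthly infection hazard, m the monthly loss hazard and T = 18. The crude proportion is l/(l+m) × (1 − exp(−(l+m)T)). Take a true 18-month risk of 20%:
- l = −ln(0.80)/18 = 0.01240
- controls: m = −ln(0.95)/18 = 0.00285; 0.8131 × (1 − 0.76) = 0.195, or 48.0 of 246
- patients at 30% loss: m = −ln(0.70)/18 = 0.01982; 0.3849 × (1 − 0.56) = 0.169, or 41.7 of 246
- crude ratio 0.169 / 0.195 = 0.87; mean person-months 15.74 and 13.66, so the ratio of infections per person-month is 1.00

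For true risks of 10% to 60% the crude ratio is 0.92 to 0.93 at 20% loss, 0.87 to 0.88 at 30% and 0.81 to 0.83 at 40%. With 5% loss in both groups it is 1.00.

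**Late infections.** Put all infections in months 12 to 18, at a true risk of 20% or 40%. The crude proportion is exp(−12m) × l/(l+m) × (1 − exp(−6(l+m))), with l now spread over 6 months. The ratio is 0.87 at 20% patient loss and 0.68 to 0.69 at 40%. The extreme case, with every infection at the end of month 18, gives 0.70 / 0.95 = 0.74 at 30% loss (0.84 at 20%, 0.63 at 40%). That is a limit, not a likely value.

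**Does one overall rate cure this?** Only if risk is constant. In the extreme late case at 30% loss, infections per person-time still give (0.70 / 0.85) / (0.95 / 0.975) = 0.85. Enrolment took less than a month (17 February to 12 March 2021, section 1.6), so study time follows calendar time closely and constant risk over 18 pandemic months is doubtful.

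**What could offset it.** At 20% true risk, detection 1.08, 1.15 or 1.23 times higher in patients cancels the deficit at 20%, 30% or 40% loss.

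**Horizon.** At constant hazard and a true 18-month risk of 20%, the 12-month proportion is 13.8%. Over true risks of 10% to 60% it is 68% to 76% of the 18-month figure.

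**The case against.** The strongest reply is that the outcome is exploratory, unpowered and descriptive, that the objective concerns patients, and that no patient/control ratio or test is planned. Section 10 also promises suitable descriptive statistics with measures of variance, so one short item need not mean that only bare counts will be published. This stands as a reason for modest weight. It does not remove the gap: a descriptive incidence still needs a denominator and a time window.

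Second, a reader might infer that patient incidence will come out too low. The documents do not support that. They give no loss by cohort; with equal loss there is no bias; and more testing of patients, or different registry consent, could offset or reverse it. Self-isolation (section 1.4) and extra vaccinations (section 1.8) may change true incidence, and person-time corrects for neither.

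Third, where follow-up ends in death, the crude proportion is a valid absolute risk with death as a competing event. That is right, but section 10.3 does not define that quantity, and withdrawal is not death.

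Three other inferences also go too far. These are not the trial's only clinical outcomes: adverse events and deaths are reported too. The 12-month wording in section 2 does not leave the analysis undefined, because section 10.3 clearly says 18 months. And the documents do not say that test dates are recorded.

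**Conclusion.** The point holds in a limited form. The objective is incidence, and the planned output cannot deliver it without denominators, time at risk and a rule for death and drop-out. If follow-up is shorter in cohorts B to D, as sections 4.2 and 4.4 suggest, crude figures can understate infection in patients relative to cohort A. The size is about 0.92 to 0.82 of the true ratio at constant risk and about 0.87 to 0.68 with infections in months 12 to 18. Both ranges rest on assumed losses of 20% to 40% against 5% and on equal detection. The net direction is not fixed, and without testing intensity and linkage rates a reader could not tell which effect dominates. The 12- versus 18-month mismatch is a wording correction. Overall this is a cheap improvement; it does not affect the primary endpoint.

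**What to change.** In section 10.3, report per cohort, descriptively and with 95% confidence intervals:
- the number at risk and the person-time;
- the cumulative incidence of first infection to 18 months after the second vaccination, with death as a competing event and censoring at withdrawal or at the last completed questionnaire or registry contact;
- infection rates by questionnaire or calendar period, rather than one overall rate, so that risk while alive and followed can be seen next to absolute risk;
- tests per person-time and the proportion consenting to RIVM linkage.

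Repeat the analysis in RIVM-linked participants. Record the date of each positive test, and use the questionnaire interval where the date is missing. Keep the planned counts and severity data.

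Change the 12 months in section 2 to match the 18 months in sections 3, 8.1.3 and 10.3. State one time origin: the Summary counts questionnaires from the second vaccination, section 11.4 from the last. Reconcile the month 12 and 15 questionnaires listed there with Table 1, which has no columns for them between days 330 and 540.

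The cost is a little extra analysis and possibly one added date field. Intervals will be wide, and the outcome stays exploratory.

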## **10.4 Interim analysis (if applicable)**

Not applicable.

#### **11. ETHICAL CONSIDERATIONS**

#### **11.1 Regulation statement**

The protocol has been written, and the study will be conducted according to the ICH Harmonized Tripartite Guideline on Good Clinical Practice (ICH-GCP, available online at https://www.ema.europa.eu/documents/scientific-guideline/ich-e6-r1-guideline-good-clinicalpractice\_en.pdf). The study will be in agreement with the principles of the Declaration of Helsinki (64, October 2013, Fortaleza, Brazil, available on the World Medical Association web site (http://www.wma.net) and with Dutch law, in accordance with the Medical Research Involving Human Subjects Act (WMO, available at https://wetten.overheid.nl/BWBR0009408/2020-01-01).

#### 11.2 Recruitment and consent

Vaccination of elderly has started in Q1 2021 in the Netherlands. In order to be able to launch this study at the time the vaccine is available, potential participants will be identified early at oncology clinics in the participating institutes and informed about:

- the aims of the study
- the potential risks of participation
- the procedures and the possible hazards to which participants will be exposed
- the obligation to register date of vaccination and type of vaccine in a national database
- otherwise strict confidentiality of any patient data
- medical records possibly being reviewed for trial purposes by authorized individuals other than their treating physician

A pre-screening Participant Information Form (PIF) will be offered. After signing prescreening informed consent (IC), baseline information will be collected and eligibility for the study will be estimated. A list of potentially eligible individuals will be created who can be contacted immediately when the vaccine is available. Potential participants will then receive the study PIF. Both the pre-screening PIF and the study PIF will be submitted to the METC along with the study protocol, there are separate versions for cancer patients (cohort B-D) and individuals without cancer (cohort A). A statement of approval should be provided before commencement of the study. Potential participants will be asked for IC by one of the investigators (a medical doctor or specialized nurse). Each subject will be given the opportunity to ask questions and will be informed about the right to withdraw from the study at any time without prejudice. Participants without an adequate antibody response after two vaccinations will be informed about the option to receive a third vaccination, a separate IC must be obtained. The formal written IC for this trial must be obtained before initiation of any study-specific procedures. Subjects must be given adequate opportunity to read the information and enquire about details of the study before consent is given. The IC procedure is done according to the ICH guidelines on Good Clinical Practice. This implies that the written informed consent form will be signed and personally dated by the participant. The informed consent statement will be signed and dated by the investigator afterwards and the subject will receive a copy. Subjects are free to decide whether or not to participate in this trial. Non-participation will not have any consequences concerning their treatment. If the patient does not want to participate in the trial, it will be enough if he/she informs one of the investigators about the decision. The decision will be documented in the (electronic) patient dossier.

#### 11.3 Objection by minors or incapacitated subjects

Not applicable.

#### 11.4 Benefits and risks assessment, group relatedness

Patients with cancer are hit harder by the COVID-19 pandemic than healthy individuals. As they have a higher risk of adverse outcome of COVID-19, many patients strictly adhere to self-isolation, resulting in loneliness and loss of quality of life. An immune response to vaccination would not only protect them from life-threatening COVID-19 but also allow close contact with their loved ones. Participation in this study gives early access to vaccination against COVID-19. For the control group, participation in the trial helps to protect their partners with cancer from getting COVID-19, and gives them early access to the vaccine. This study will generate highly valuable information on the ability to mount an effective immune response during cancer treatment that can guide management of cancer patients during the pandemic worldwide.

Participants without an adequate antibody response will be offered a third vaccination. Most participants in the VOICE study showed an increase in SARS-CoV-2-binding antibody concentration following a second vaccination, a third vaccination will therefore likely further increase the antibody response. Patients with cancer could therefore benefit from better protection induced by a third vaccination. A third vaccination with another mRNA vaccine (BNT162b2, Pfizer-BioNTech) in 101 solid organ transplant recipients showed that from the 59 patients who did not have SARS-CoV-2 specific antibodies before the 3rd vaccination, 44% was seropositive 28 days after the third vaccination. Patients who were already seropositive before the third vaccination showed a significant increase in antibody concentration. No serious adverse events were reported after the administration of the third dose, and no acute rejection episodes occurred [43]. The FDA

on August 12th authorized additional mRNA-1273 and BNT162b2 vaccine doses for immunocompromised individuals, administered at least 28 days after the two-dose regimen of the same vaccine [44]. Recently, Moderna requested a general FDA approval for a third dose of mRNA-1273, based on a study in 344 volunteers [45]. Currently both mRNA-1273 and BNT162b2 are used for third vaccinations in immunocompromised patients and for boosters in the Netherlands.

Participation in this study requires 6 hospital visits at which blood will be drawn by venipuncture and 2 non-invasive collections of nasal mucosal lining fluid are performed. Maximum 3 additional hospital visits are required for participants who will receive a third vaccination. Participants have to fill in a questionnaire at baseline, and at 3, 6, 9, 12, 15 and 18 months after the last vaccination. Participants will be informed about their antibody titer in a letter that includes an explanation about what this means to them. This will be done after antibody measurements have been completed for day 28 after vaccination, and again after 6, 11 and 18 months after the second vaccination. Participants who receive 3 vaccinations will also receive their antibody concentration on day 28 after the third vaccination. Potentially eligible subjects who decide not to participate in the study will have access to the general Dutch vaccination program, which now includes a third vaccination as part of the primary vaccination in immunocompromised patients and a booster for everybody at a minimum of 3 months after completion of the primary vaccination.

#### **11.5 Incentives (if applicable)**

For each day of subject related study procedures, the subjects will receive compensation for travelling expenses ( $\notin 0.19$ /km) and parking.

#### **12. ADMINISTRATIVE ASPECTS, MONITORING AND PUBLICATION**

#### 12.1 Handling and storage of data and documents

Study subjects will receive a code. The key to the code (number linked to patient) is safeguarded by the investigator. The study code assigned to the patients will be used in the collection of all the study results by IKNL (Integraal Kankercentrum Nederland).

An overview of all data and data-analysis is made according to this code, so that the final results cannot be traced back to the patients by another person than the investigators involved in the study (in compliance with the Dutch Personal Data Protection Act). For the study participants who give separate consent, information on positive COVID-19 tests

during the study will also be collected from the RIVM. Data will be stored for a maximum period of 15 years after the study is finished.

